11.4. Subject Disposition and Baseline Characteristics

The numbers of patients screened and enrolled will be summarized. Reasons for screen failures will be presented. The number of patients receiving ataluren will be described. Patients who do not complete the planned observations will be described and evaluated separately. Patients receiving ataluren who are found not to have fully met the eligibility criteria will be described. On-study protocol violations will also be presented. Reasons for study discontinuation and dates of withdrawal from study will be described.

Patient characteristics at baseline will be summarized using appropriate descriptive statistics.

11.5. Efficacy Endpoints

Observed values and changes from baseline in timed function tests, NSAA total score and composite score will be summarized descriptively.

11.6. Pharmacokinetic Parameters

PK parameters of ataluren on Day 1 and 28 will be derived using non-compartmental analysis (NCA) methods. The PK parameters of ataluren listed below will be derived following the morning dose on Day 1 and 28 using NCA methods.

Parameters	Definition
AUC _{0-t}	Area under the plasma concentration time curve from time zero to the time of last quantifiable concentration (C _{trough}) using the linear trapezoidal rule during the ascending portion of the curve and the log-trapezoidal rule during the descending portion of the curve
AUC ₀₋₁₀	Area under the plasma concentration time curve from time zero up to 10 hours after the morning dosing using the linear trapezoidal rule during the ascending portion of the curve and the log-trapezoidal rule during the descending portion of the curve
C _{max}	Maximum observed plasma concentration
C _{trough@6h}	Concentration at the end of the first (morning) dosage interval
t _{max}	Time of maximum observed plasma concentration
λ _z	Terminal rate constant
t _{1/2}	Terminal half-life, calculated as ln(2) / λ _z

The accumulation ratio on Day 28 will be calculated as follows:

Parameter	Description
AR(AUC)	$AR(AUC) = (AUC_{0-t})_{Day28} / (AUC_{0-t})_{Day 1}$
AR(C _{max})	$AR(C_{max}) = (C_{max})_{Day28} / (C_{max})_{Day 1}$

Individual PK parameters will be derived using actual sampling and dosing times. Concentrations below the limit of quantitation (LOQ) will be set to zero for the calculation of NCA parameters. PK parameters will be summarized with descriptive statistics on Day 1 and 28 (eg, n, arithmetic mean, standard deviation, standard error, median, minimum, and maximum, CV% mean, geometric mean, and CV% geometric mean). The analysis will be performed with a fully validated version of Phoenix WinNonlin V6.3.

In addition, a popPK analysis will be performed by simultaneously assessing concentrations on Days 1 and 28 in order to explore the potential time-dependency of ataluren and derive the following additional PK parameters.

Parameter	Description
ka	Rate constant of absorption
CL/F	Apparent clearance
CLd/F	Apparent distribution clearance
Vc/F	Apparent volume of distribution
Vp/F	Apparent peripheral volume of distribution

The above PopPK model will be used to simulate rich concentration-time profiles and derive the area under the curve over 24 hours (AUC_{0-24}).

A two-compartment model with time-dependent clearance (between the morning and midday dose), was previously used to assess the concentration-time profiles of ataluren in adult patients with nonsense-mutation Duchenne-Becker muscular dystrophy. If required, data collected in the current study (≥ 2 to < 5 year old nmDMD patients) may be merged with data collected in adult patients with nmDMD to assess potential effect of age and/or body weight on PK parameters of ataluren.

Additional information will be provided in the PK analysis plan.

11.7. Safety

11.7.1. Adverse Events

Adverse events will be tabulated by using the MedDRA classification system. The severity of the AE will be graded using the CTCAE whenever possible. For AEs that are not included in the CTCAE, the grading categories (mild, moderate, severe, life-threatening, and fatal) described in Table 4 will be used. The frequency of patients experiencing a specific AE will be tabulated by system organ class; preferred term; seriousness (serious vs nonserious; see Section 9.1.2); timing of occurrence, outcome, and relationship to study drug (see Section 9.4); and worst severity (see Section 9.5) In the by-subject analysis, a patient having the same event more than once will be counted only once and will be classified at the highest severity and/or relatedness for those events.

Adverse events classified as CTCAE Grade ≥ 3 ; study-drug-related events; hepatic, and renal events leading to special diagnostic evaluations; events leading to discontinuation of ataluren, events leading to death, and SAEs will be considered with special attention.

11.7.2. Laboratory Parameters

Hematological and biochemistry data will be summarized by visit and will be graded according to CTCAE severity grade, when applicable. The frequencies of the worst severity grade observed will be displayed. For variables graded according to CTCAE severity grade, the frequencies of

the worst severity grade observed will be displayed. For parameters for which a CTCAE scale does not exist, the frequency of patients with values below, within, and above the normal ranges will be summarized. In the by-subject analysis, a patient having the same abnormality more than once will be counted only once based on the worst severity grade observed.

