8.2.7.3. Urinalysis

Urinalysis will include analysis for pH, specific gravity, glucose, ketones, blood, protein, urobilinogen, bilirubin, nitrite, and leukocyte esterase. These parameters will be measured at every protocol-specified study visit. The study manual should be referenced for collection, processing, and shipping information.

8.2.8. 12-Lead ECG

A 12-lead ECG will be obtained at screening, Week 4 (Visit 3), Week 52 (Visit 7/ET), and 4-week Follow-up (Visit 8). ECGs will be read locally at investigational sites and interpreted for clinical significance. The findings will be captured in source documents and within the eCRF.

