11.3. General Statistical Considerations

By-subject listings will be created for each eCRF module. Summary tables for continuous variables will contain the following statistics: N, mean, median, standard deviation, standard error, minimum, maximum, and 95% confidence intervals (CIs) as appropriate. Summary tables for categorical variables will include N and percentage. Graphical techniques will be used when such methods are appropriate and informative.

Transformations of the data may be explored if warranted by the distribution of the data.

All analyses will be performed using Statistical Analysis System (SAS® Version 9.0 or higher).

The primary analysis will be conducted on data obtained during the 4-week PK period of the study and may be reported separately from the extension study data.

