14.2.4. Safety Monitoring

In defining therapeutic activity in a particular clinical setting, it is imperative that the drug's safety profile be fully characterized. As is conventional in all clinical studies, proper description of each AE or laboratory abnormality requires an understanding of the type, incidence, timing, severity, and relatedness to study drug. In this study, particular focus will be placed on monitoring for renal adverse findings. For consistency of interpretation, AEs will be coded using the standard MedDRA, and the severity of these events will be graded using the well-defined CTCAE Version 4.0. Standard definitions for seriousness will be applied. Particular attention will be paid to any AEs causing discontinuation of ataluren and to SAEs requiring rapid regulatory reporting.

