12.2. Clinical Laboratory Assessments

Laboratory assessments performed during each study visit and will include hematology, biochemistry and urinalysis. The presentation of laboratory results focuses on the descriptive summaries at Baseline, each scheduled follow-up evaluation, and the change from baseline. All subjects in the Safety Population who have a baseline and at least one follow-up laboratory assessment will be included in the presentation of the laboratory data. In order for a subject to be included in the analysis for a particular laboratory test, the subject must have a baseline value and a follow-up laboratory assessment for the laboratory test. Unscheduled laboratory evaluations will be presented in the listings. The summarized results will be presented for the 4 week primary PK period of the study and for the extension study data.

For each quantitative laboratory parameter, the baseline results will be summarized using descriptive statistics: n, mean, SD, median, and range. Only paired quantitative data will be summarized in the tables; all data will be presented in the listings. Results will be summarized and presented in Tables 14.3.6.1 entitled *Summary of Hematology Results by Visit* (Safety Population), 14.3.6.2 entitled *Summary of Biochemistry Results by Visit* (Safety Population), and 14.3.6.3 entitled *Summary of Urinalysis Results by Visit* (Safety Population).

Laboratory shift tables will be prepared and presented based on the normal reference ranges and presented by parameter and the scheduled observation time. Shift tables will be prepared and presented for each quantitative hematology parameter in Table 14.3.6.4 entitled *Hematology Shift Table Results by Visit* (Safety Population). Shift tables will be prepared and presented for each quantitative biochemistry parameter in Table 14.3.6.5 entitled *Biochemistry Shift Table Results by Visit* (Safety Population). Shift tables will be prepared and presented for each

quantitative urinalysis parameter in Table 14.3.6.6 entitled *Urinalysis Shift Table Results by Visit* (Safety Population).

The supportive data for Tables 14.3.6.1 through 14.3.6.6 are presented in Listing 16.2.8.4 entitled *Hematology Results*, Listing 16.2.8.5 entitled *Biochemistry Results*, and Listing 16.2.8.6 entitled *Urinalysis Results*. These listings will be sorted by subject number, parameter, and relative day.

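### Under SAP 12.2, urine results reported as categories would be listed but not tabulated, and the urine protein rows of SAP Table 3 cannot be filled from the collected panel

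*Protocol*

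**What the plan says.** **Collection.** Protocol 8.2.7.3: "Urinalysis will include analysis for pH, specific gravity, glucose, ketones, blood, protein, urobilinogen, bilirubin, nitrite, and leukocyte esterase". It adds "These parameters will be measured at every protocol-specified study visit", and the schedule of events marks urinalysis at all 8 visits. No assay method or reporting format is given for any analyte. SAP 3.4.1 repeats the same 10 analytes.

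**Analysis in the protocol.** Section 11.7.2 opens with "Hematological and biochemistry data will be summarized by visit and will be graded according to CTCAE severity grade, when applicable". Urinalysis is not mentioned there. The same section has a fallback rule: "For parameters for which a CTCAE scale does not exist, the frequency of patients with values below, within, and above the normal ranges" are to be summarized. Section 11.3 gives a general rule: "Summary tables for categorical variables will include N and percentage".

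**Analysis in the SAP.** Section 12.2 brings urinalysis in and plans three tables that could hold urine data:

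- Table 14.3.6.3, a summary by visit. The rule governing it is "Only paired quantitative data will be summarized in the tables; all data will be presented in the listings".
- Table 14.3.6.6, a shift table, prepared for each "quantitative urinalysis parameter in Table 14.3.6.6".
- Table 14.3.6.7, abnormalities in the variables pre-defined for safety monitoring. The text leads directly into SAP Table 3. The urine rows there are blood by dipstick, the spot protein to creatinine ratio, and the spot protein to osmolality ratio.

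**Importance.** Protocol 3.3 places laboratory abnormalities, including their frequency, severity and timing, in the primary endpoint. Protocol 14.2.4 states: "In this study, particular focus will be placed on monitoring for renal adverse findings".

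**The concern.** A urine panel usually mixes numeric results with results read as grades or as negative/positive. The SAP's wording admits only the numeric ones to the by-visit and shift tables. For anything else, SAP 12.2 gives a rule rather than leaving a gap: the result goes to a listing. A listing shows individual values but gives no frequency, no denominator and no shift from baseline, and those are what the primary endpoint calls for.

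Urine protein matters most here because of the declared renal focus. Whether it is tabulated depends on a reporting format that neither document states. The one table that could rescue it, 14.3.6.7, defines protein abnormality through quantities that the study does not plan to collect. Low-grade new proteinuria or glycosuria that prompts no work-up could therefore go uncounted in every table, while pH and specific gravity are summarized in full.

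**Working it through.** The plan gives no figure to reproduce. The check sets the collected urine panel against each planned table and then counts results.

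**Step 1: which table can hold which result.**

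| Urine result | 14.3.6.3 and 14.3.6.6 | 14.3.6.7 (via SAP Table 3) |
|---|---|---|
| pH, specific gravity (numeric) | yes | no row |
| Blood, as dipstick grade | no | yes (2+, 3+, 4+) |
| Protein, if numeric | yes | no row for the result itself |
| Protein, if a category | no | no row for the result itself |
| Glucose and the other 5 analytes, if categories | no | no row |

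**Step 2: range over the unknown format.** The panel has 10 analytes. If all are reported as numbers, all enter 14.3.6.3 and 14.3.6.6, and 0 are left out. If only pH and specific gravity are numeric, 2 enter those tables, 1 more (blood) enters 14.3.6.7, and 10 − 2 − 1 = 7 reach no laboratory summary table. Protein and glucose are among the 7. The documents do not settle where in the range 0 to 7 the study falls.

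**Step 3: the protein rows of SAP Table 3.** The thresholds are >0.40 mg:mg for protein to creatinine and >0.30 mg/L:mOsm/kg for protein to osmolality. Each ratio needs a denominator measured in urine. The panel in Protocol 8.2.7.3 and SAP 3.4.1 contains neither urine creatinine nor urine osmolality; the creatinine in the biochemistry panel is listed with the serum analytes. Neither ratio can be computed from planned data. This holds whatever the format of the protein result.

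**Step 4: number of protein results affected if protein is a category.** Inputs are 12 patients (Protocol 11.1), urinalysis at every visit, Day 1 (Visit 2) as baseline, and no dropout (an assumption). Results = patients × post-baseline visits.

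- 4-week primary analysis (Protocol 11.3), Visit 3 only: 12 × 1 = 12.
- On treatment, Visits 3 to 7: 12 × 5 = 60.
- Including the follow-up visit 4 weeks after treatment, Visits 3 to 8: 12 × 6 = 72.

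**Step 5: do the general rules fill the gap?** Protocol 11.3 and SAP 5 both provide counts and percentages for categorical variables. SAP 12.2 is the specific rule for laboratory data and excludes non-quantitative results from the tables, so a programmer following it would not apply the general rule. The fallback sentence in Protocol 11.7.2 follows a sentence confined to hematology and biochemistry. Even read broadly, the SAP carries it out for urine only through a shift table limited to quantitative parameters.

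**The case against.** A reader might infer that protein is certainly read by dipstick and so certainly reaches no summary table. The documents do not support that. They attach the word dipstick only to urine blood, send all samples to a central laboratory, and give urine protein only in numeric ratio form. If protein is reported as a number, it enters both 14.3.6.3 and 14.3.6.6. This objection stands and makes the tabulation point conditional. It does not touch the ratio rows.

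A reader might also infer that the SAP tabulates nothing but quantitative urine data. That is wrong for blood, which has graded rows behind 14.3.6.7. The scope of that table is itself not quite clear: its supporting listings include abnormal hematology, although SAP Table 3 has no hematology row. The text nevertheless describes pre-defined variables, and no other pre-definition is given.

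Nor would all new proteinuria be invisible in the safety tables. SAP 3.4.1 reports abnormal laboratory tests as adverse events, and renal events also feed Table 14.3.1.7. Protocol 9.1.1 narrows that route: abnormalities needing neither intervention nor further investigation are not adverse events and belong to laboratory monitoring. So the route catches results that lead to a work-up and misses the rest.

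The figure of 72 should not be read as the loss in the primary analysis, which holds 12 planned post-baseline results.

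Finally, renal monitoring does not rest on urine alone. Serum creatinine, BUN and cystatin C are collected at every visit and have thresholds in SAP Table 3. With about 12 boys, the abnormal-value listing (14.3.7.3) can be read through. Both points stand: what is at risk is the summary, not the data. They do not explain why a panel done at every visit should lack counts.

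**Conclusion.** The point holds in two parts.

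1. **Conditional.** If urine analytes are reported as categories, SAP 12.2 keeps them out of the by-visit and shift tables, and only blood is picked up elsewhere. Up to 7 of 10 analytes have no laboratory summary table. For protein, up to 12 post-baseline results are affected in the 4-week analysis, 60 on treatment and 72 with follow-up, assuming 12 boys and no dropout. If protein is numeric, these protein counts fall to zero.
2. **Unconditional.** The two urine protein rows of SAP Table 3 cannot be filled from the planned panel, so the collected protein result has no pre-defined abnormality category in Table 14.3.6.7.

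The omission of urinalysis from Protocol 11.7.2 is secondary, since the SAP does bring it in. The change is worth making because laboratory abnormalities are in the primary endpoint, renal findings are a stated focus, and the remedy is cheap. Confidence is high on the ratio rows and moderate on the tabulation gap, which turns on the unstated format.

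**What to change.** - Name urinalysis in Protocol 11.7.2 beside hematology and biochemistry.
- State in SAP 12.2 how each urine analyte is reported.
- Extend Table 14.3.6.6 from quantitative to all urinalysis parameters, with categorical results shown as counts and percentages by visit.
- For protein, blood and glucose, also show baseline category against worst post-baseline category, counting each boy once.
- Treat unscheduled samples as in the other laboratory tables. SAP 12.2 currently sends them to listings, and a different rule for urine alone would need its own justification.
- Reconcile the two protein-ratio rows of SAP Table 3 with the collected urine panel. That table also carries study-drug actions, and this point takes no position on those.

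The tabulation changes need wording and one extra categorical table, using data already collected. What the ratio rows require depends on how the sponsor reconciles them.

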11.7.3. Vital Signs and ECGs

Vital signs (height, weight, BMI, pulse rate, and body temperature) and ECGs will be listed and summarized by visit. Where appropriate, changes from baseline will be presented by visit.

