Ataluren has been administered to patients with nonsense mutation cystic fibrosis (nmCF) as young as 6 years of age, patients with nmDMD as young as 5 years of age, and patients with nonsense mutation methylmalonic acidemia (nmMMA) as young as 3 years of age. No obvious differences have been apparent in the activity or safety profiles of ataluren in children relative to adults. Although patients <3 years of age have not been included in clinical studies, chronic toxicology studies in weanling rats and dogs support dosing of pediatric patients as young as 2 years of age. Refer to the Ataluren Investigator's Brochure (IB) for current information on use in pediatric patients.

This protocol describes a Phase 2, multiple-dose, open-label study evaluating the safety, pharmacokinetics (PK), and pharmacodynamics (PD) of ataluren in patients aged ≥ 2 to <5 years old with nmDMD. In nmDMD, early start of treatment is important and necessary and, therefore, it is relevant to understand the correct and tolerable dose in this age group, particularly since ataluren is dosed by weight. The study will include a 4-week screening period, a 4-week study period, and a 48-week extension period for patients who complete the 4-week study period (52 weeks total treatment). The objective of the extension period is to assess the long-term safety of chronic administration of ataluren in this patient population.

The primary objective of this study is to evaluate the safety of ataluren as measured by type, frequency, severity, timing, and relationship to study drug of treatment-emergent adverse events (TEAEs), laboratory abnormalities, and electrocardiograms (ECGs).

The secondary objectives are to determine the plasma PK of ataluren in patients aged ≥ 2 to < 5 years old with nmDMD, to monitor proximal muscle function using timed function tests (TFTs), to monitor physical function using the North Star Ambulatory Assessment (NSAA), to determine the effect of ataluren on weight, height, and body mass index (BMI), and to assess the palatability of ataluren.

This study provides ongoing safety review during open-label ataluren treatment. Furthermore, a planned interim safety analysis will be conducted by an independent data monitoring committee (DMC) when all patients have completed 12 weeks of treatment and additionally as needed.

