3.2. Secondary Objectives

The secondary objectives of this study are to:

- Evaluate the plasma PK of ataluren in patients aged ≥ 2 to < 5 years old with nmDMD
- Assess proximal muscle function using TFTs
- Assess change in physical function using the NSAA
- Determine the effect of ataluren on weight, height, and BMI
- Assess the palatability of ataluren

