3.4. Secondary Endpoints

The secondary endpoints are:

- Pharmacokinetic parameters (t_{max} , $t_{1/2}$, C_{max} , $C_{trough@6h}$, AUC_{0-10}), CL/F, and V_c/F based on frequent blood sampling for PK on Days 1 and 28 of ataluren treatment. On each of these days, blood samples for ataluren concentration assessments will be collected immediately pre-dose and at specified time points following the morning, midday, and evening doses. Ataluren concentrations in plasma will be analyzed using a validated HPLC-MS/MS method.
- TFTs (time to walk/run 10 meters, time to climb 4 stairs, time to descend 4 stairs, and time to stand up from a supine position)
- NSAA
- Changes in body weight, height, and BMI
- Ataluren palatability characteristics as determined by a parent/caregiver questionnaire

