6.2. Study Drug Treatment

6.2.1. Study Drug Dosing

Dosing of ataluren will be based on milligrams of drug per kilogram of patient body weight assessed every 12 weeks. All patients will receive approximately 10, 10, 20 mg/kg ataluren 3 times daily (TID) for 4 weeks during the PK portion and for 48 weeks during the extension period.

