3. STUDY OBJECTIVES AND ENDPOINTS

3.1. Study Objectives

The primary objective of this study is to evaluate the safety of ataluren as measured by type, frequency, severity, timing, and relationship to study drug of treatment emergent adverse events (TEAEs), laboratory abnormalities and electrocardiograms (ECGs).

There are 5 secondary objectives of the study, presented in the order from section 3.2 of the protocol:

- Evaluate the plasma pharmacokinetics (PK) of ataluren in subjects aged ≥ 2 to < 5 years old with nmDMD
- Assess proximal muscle function using timed function tests (TFTs)
- Assess change in physical function using the North Star Ambulatory Assessment (NSAA)
- Determine the effect of ataluren on weight, height, and body mass index (BMI)
- Assess the palatability of ataluren

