12.3. Vital Signs

All vital signs will be taken each visit and include the following parameters:

- Pulse Rate (beats per minute)
- Temperature (°C)
- Respiratory Rate (breaths/min)
- Systolic Blood Pressure (mmHg)
- Diastolic Blood Pressure (mmHg)

Vital signs will be summarized for each clinical assessment using the summary statistics of n, mean, SD, median, and range. These summaries will be presented for the subjects who have data at baseline and the specific follow-up visit. The summarized results will be presented for the 4 week primary PK period of the study and for the extension study data. The organization of the

results is commensurate with the organization of the laboratory data. All subjects in the Safety Population who have a baseline and at least one follow-up vital sign assessment will be included in the presentation of the data. In order for a subject to be included in the analysis for a particular evaluation, the subject must have a baseline value and a follow-up assessment. Unscheduled laboratory evaluations will be presented in the listings. The summarized results will be presented for the 4 week primary PK period of the study and for the extension study data. The results will be presented in Table 14.3.3 entitled *Summary of Vital Sign Results by Visit* (Safety Population). The supportive data listing is Listing 16.2.8.1 entitled *Vital Signs*. This listing will be sorted by subject number, parameter, and relative day.

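### Raw change in height, weight and BMI is hard to interpret in a single arm of growing boys; age- and sex-standardised z-scores would describe growth better, though they would not isolate an effect of ataluren

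*Protocol*

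**What the plan says.** Protocol 3.2 sets the secondary objective: "Determine the effect of ataluren on weight, height, and BMI". SAP 3.1 repeats it. The matching endpoint in Protocol 3.4 is "Changes in body weight, height, and BMI".

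The only stated method is in Protocol 11.7.3: "Vital signs (height, weight, BMI, pulse rate, and body temperature) and ECGs will be listed and summarized by visit". It adds: "Where appropriate, changes from baseline will be presented by visit". Protocol 11.3 supplies the general descriptive statistics, including 95% confidence intervals as appropriate.

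SAP 12.3 introduces its list with "All vital signs will be taken each visit and include the following parameters". The list contains pulse, temperature, respiratory rate and the two blood pressures. Height, weight and BMI are not in it, and no table or listing title in SAP section 14 names them.

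The study is open-label (Protocol 1), and all patients receive the same regimen (Protocol 6.2.1). The natural history extract in SAP 3.9 covers demographics at entry, timed function tests and NSAA. It names no follow-up height, weight or BMI. Neither document mentions a z-score, a percentile or a growth reference.

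**The concern.** The objective asks about an effect, but the stated summary has nothing to set the result against. All boys are expected to grow over 52 weeks, so a mean increase in height or weight is expected with or without a drug effect. Entry ages span up to three years, so the expected gain also differs between boys, and the mean depends partly on who enrols.

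BMI behaves differently. Height and weight rise together, so the expected change can be small and of either sign. Its size depends on age and starting point, so zero is not a safe reference for BMI either.

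At stake is one of five secondary objectives, and a growth description that bears on the stated purpose of the extension, long-term safety. A moderate slowing of growth would still appear in the summary as a positive mean change.

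**Working it through.** **Inputs from the documents.** Boys aged 2 to <5 years (Protocol 4.2); 52 weeks on treatment (Protocol 6.2.2); 12 patients, with no formal statistical basis (Protocol 11.1); height and weight at all eight visits (Protocol 8.2.5 and Table 2); age in months and years (SAP 8.1). The plan has no growth figure to reproduce: it gives no growth rate, SD, target effect or precision for this endpoint.

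**Assumptions, none from the documents.** Normal height gain 5 to 9 cm over 52 weeks; drug-related deficit 0.5 to 2 cm; SD of raw height change 1.5 cm; between-boy SD of height 4 to 5 cm; SD of z-score change 0.2 to 0.8.

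**1. Raw height change.**
- The deficit is between 0.5/9 = 6% and 2/5 = 40% of the expected gain.
- The 95% CI half-width for a mean is t(0.975, n−1) × SD/√n. For n=12 this is 2.201/3.464 = 0.635 × SD. With SD 1.5 cm it is 0.95 cm.
- Growth of 7 cm with no effect gives a mean of 7 cm (6.05 to 7.95). Growth of 9 cm with a 2 cm deficit gives 9 − 2 = 7 cm, with the same interval. The raw table cannot tell these apart.

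**2. Raw BMI change**, as weight (kg)/height (m)², with assumed starting values and gains:
- 88 cm and 12.5 kg, gaining 8 cm and 2 kg: 12.5/0.88² = 16.14 to 14.5/0.96² = 15.73, change −0.41.
- 95 cm and 14 kg, gaining 7 cm and 1.5 kg: 15.51 to 15.5/1.02² = 14.90, change −0.61.
- 95 cm and 14 kg, gaining 7 cm and 2.5 kg: 15.51 to 16.5/1.02² = 15.86, change +0.35.

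Expected growth gives changes of −0.61 to +0.35 kg/m², so it does not dominate BMI as it does height and weight. A raw BMI change still has no clear reference value.

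**3. Precision of a mean z-score change.** The half-width is as above. The change detectable with 80% power (two-sided 0.05, noncentral t) is 0.889 × SD at n=12.

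| Assumed SD of z-score change | 95% CI half-width | Detectable change |
|---|---|---|
| 0.2 | 0.13 | 0.18 |
| 0.3 | 0.19 | 0.27 |
| 0.5 | 0.32 | 0.44 |
| 0.8 | 0.51 | 0.71 |

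With 10 evaluable boys the factors are 0.715 and 0.996; with 8 they are 0.836 and 1.156.

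A 1 cm deficit is 1/5 = 0.20 to 1/4 = 0.25 z. A 2 cm deficit is 2/5 = 0.40 to 2/4 = 0.50 z. At SD 0.3 the larger deficit is detectable and the smaller is not. At SD 0.5 the larger is borderline.

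**4. What a z-score leaves in.** Simulation with n=12, 20,000 runs and a true drug effect of zero gave the share of runs in which the 95% CI for mean z-score change excludes zero:

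| Assumed source of change | SD 0.3 | SD 0.5 |
|---|---|---|
| None | 5% | 5% |
| Disease drift −0.1 | 18% | 10% |
| Disease drift −0.2 | 56% | 24% |
| Disease drift −0.3 | 88% | 47% |
| Half the boys start corticosteroids, effect −0.3 | 29% | 15% |

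A z-score change different from zero is therefore not evidence of a drug effect by itself.

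**5. Age range needed.** Boys are up to 5 + 364/365.25 = just under 6.0 years at Week 52, and up to 5 + 392/365.25 = about 6.07 at Week 56. A reference that stops at 5 years would not cover the older boys.

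**The case against.** The strongest objection is that z-scores do not deliver the stated objective either. They compare these boys with reference children, not with untreated boys with DMD. Growth typical of the disease stays mixed with any drug effect. So do corticosteroid changes: Protocol 7.1.1 lets patients stay on study drug through them, and Protocol 2.1 puts usual initiation at about age 5, which older boys reach on study. This stands, and the simulation shows its size. A reader might infer that z-scores would answer the question of an effect on growth; the documents do not support that in a single-arm study.

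A reader might also infer that a growth problem would go unseen. That is too strong. Protocol 11.3 plans by-subject listings for each eCRF module, Protocol 9.1.1 makes abnormalities needing intervention or investigation reportable as adverse events, and an independent DMC reviews safety. A very large effect could also be recognised in raw data. If growth were halved from an assumed 5 to 8 cm, the gain would be 2.5 to 4 cm, a range that does not overlap the expected one. That recognition would still need an outside reference, which the plan does not name.

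Finally, this is a small descriptive study and growth is one of five secondary objectives. That limits the weight of the point but does not remove it.

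**Conclusion.** The concern holds in a limited form. Raw change in height and weight has no no-effect value in this design, and raw BMI change depends on age. The summary in Protocol 11.7.3 is therefore hard to interpret for the growth objective. No growth comparator is planned, and the SAP does not list these measures. That part rests on the documents alone.

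Z-scores are a better description from data largely in hand, not a route to a causal answer. Their size of benefit depends on assumed growth rates and SDs. At n=12 only the larger of the deficits considered would be detected reliably.

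It would also go too far to say that growth is left unanalysed, since Protocol 11.7.3 does commit to a summary. I class this as a cheap improvement.

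**What to change.** In Protocol 11.7.3 and the SAP:

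- Add height, weight and BMI explicitly to the SAP's analyses, tables and listings.
- Convert each value to a z-score for age and sex, using one named growth reference that covers 2 to about 6 years, including the Week 56 visit.
- Derive age at each visit from birth date, or from age at screening, and the visit date. The schedule of events has no age row.
- Report change from baseline in z-score with 95% CI by visit, shown by corticosteroid use and alongside the raw values. Subgroup intervals will be wide and should be read descriptively.
- State that the result describes growth relative to reference children and is not a causal effect of ataluren. Reword the objective in Protocol 3.2 and SAP 3.1 to match.

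The cost is a few derived variables, one or two tables and some wording; no new procedure or visit is needed. The downsides are dependence on the chosen reference population and limited precision with 12 boys.
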